Effects of exercise training on the autonomic nervous system in CHF.....	10
Hypothesis.....	10
Objectives.....	11
Routine medical examination	12
Cardiopulmonary Exercise Test.....	12
24-h Holter ECG recording	12
Echocardiography	12
Endothelial Function	13
Blood Sample Analysis	13
Rehabilitation Program: MICE and HIIT training mode.....	13
Primary and secondary endpoints	14
Primary endpoint	14
Secondary Endpoint	14
Design of the study	15
Randomization	15
Eligibility criteria (inclusion / exclusion)	15
Recruitment	15
Expected fallout	16
Statistics	17
Sample Size	17
Statistical analyses	17
Research Calendar	18
Specific terms of monitoring.....	19
Rules for stopping research	19
The final stop rules.....	19
Research Monitoring Committee.....	20
Ethical and regulatory compliance.....	21
References	22

Abbreviations List

ANS : autonomic nervous system

CHF : chronic heart failure

HIIT : high intensity interval exercise training

HR : heart rate

HRR : heart rate recovery

HRV : heart rate variability

MAP : maximal aerobic power

MICE : moderate intensity and continuous exercise training

RMSSD : root mean square successive difference of heart rate

SDNN : Standard Deviation of Normal-Normal interbeat interval

VO2 max : maximal oxygen consumption

Scientific Background

Chronic Heart Failure : definition and epidemiology

[figure not shown]
[figure not shown]
Chronic Heart Failure (CHF) is defined as a structural or functional abnormalities of the heart leading to insufficient oxygen supply to the tissues. The prevalence is estimated between 2 and 3% in Europe by the European Society of Cardiology and increases sharply with age from 75 years [1]. Despite a significant reduction in mortality between 2000 and 2010, CHF remains a common cause of death, especially among the elderly [2]. In France, the mortality rate is 60% in the five years following diagnosis [2] and up to 40% of CHF patients die within one year of their first hospitalization [3].

It is estimated that nearly half of the deaths related to the pathology are due to rhythm disorders leading to sudden cardiac death. The role of the autonomic nervous system (ANS) and in particular the imbalance of the sympatho-vagal balance is recognized as a main factor in the occurrence of a number of rhythm disorders that can lead to sudden cardiac death [4].

Chronic Heart Failure and the autonomic nervous system

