The rehabilitation program focus on controlling cardiovascular risk factors, diet monitoring, therapeutic education sessions and psychological support when needed. In our clinical center, the RP last 3 hours per day, 5 days per week during 3.5 weeks. The daily activity training include a cycling endurance training (HIIT or MICT), a 30-min of gymnastics or muscle strengthening (3 series of 15 repetitions at 50% of 1-repetition maximum test in chest press, leg press, pull over, low row, leg extension) and 45-min outside walking sessions. Each session will be monitored by a physiotherapist and was supervised by a cardiologist.

The HIIT consist of two sets of 8-min intervals at 100% of peak power output (PPO) [24, 26]. Each interval set is composed of repeated bouts of 30 s at 100% of PPO interspersed by 30 s of passive recovery in the seated position. Four minutes of passive recovery are allowed between the two sets. The MICT training consist of cycling 30 minutes at 60% of peak power output. Each mode of training start with 5 minutes of warm up and finish with 5 minutes of cool down at 30% of PPO.

Primary and secondary endpoints

Primary endpoint

Evolution between day 0 (D0) and Week 4 (W4), of the High Frequency component of HRV measured during the night time period and expressed in normalized units (%): HF nu%.

Secondary Endpoint

The analysis will also focus on the evolution of the following variables:

Variables extracted from the analysis of the HRV (Holter-ECG 24h)

Heart Rate rest (beats per minute - bpm)

LF, HF (milliseconds², standard units)

VLF (milliseconds²)

Total Spectral Power (milliseconds²)

SDNN (milliseconds)

rMSSD (milliseconds)

LF / HF ratio

Number and nature of arrhythmias

Variables of echocardiography

Size of the cardiac cavities (diameter (mm), surface (cm²), volume (ml.m²))

LV systolic function (Ejection fraction (%), parietal thickness (mm))

Filling LV (E / A, E / e', Ap-Am (ms), E / Vp)

Systolic function of RV (shortening fraction (%), S'wave (cm.s), systolic excursion of tricuspid ring (mm))

Variables of the cardiopulmonary exercise test

Maximum oxygen consumption (VO₂pic (ml.min))

Maximum heart rate (bpm)

Heart rate after 1 minute, 2 minutes and 3 minutes of passive recovery

Oxygen pulse (ml.min.batt)

Slope VE / VCO₂

Maximum aerobic power (watts)

Variables of endothelial function

Reactive Hyperemia Index (RHI)

Variables of the blood test

Blood glucose (mmol.L); HbA1c (%)

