Total duration of the research: 3 years

Summary table of patient follow-up

	Pre-inclusion D- 1 à D- 2	Inclusion D 0 +/- 2 days	Week 4 +/- 3 days
eligibility criteria	✓		
Patient information of the research	✓		
Collection of sign informed consent		✓	
Randomization		✓	
Clinical Exam ¹ (Nurse)		✓	✓
Holter ECG-24h (nurse)		✓	✓
Endothelial function (nurse)		✓	✓
Biological assessment 2 (nurse)		✓	✓
Echocardiography (cardiologist)		✓	✓
Cardiopulmonary exercise test (cardiologist)		✓	✓

¹Clinical examination: measurement of: height, weight, analysis of body composition by impedance, measurement of waist circumference and resting blood pressure.

²Biological assessment: lipid balance, glycemic, adrenaline, norepinephrine, NT-pro-BNP, beta hCG for women(D0).

Specific terms of monitoring

In addition to the usual medical care of the patient, a Supervisory Committee will ensure the proper conduct of research, the safety of proposed programs. , Any adverse effects caused by physical exercise training (muscle pain cramp, fatigue of the patient), change of drug treatment, compliance with the protocol will be noted in the medical file. In case of fatigue of a patient or for medical or paramedical reason, the exercise training intensity may be reduced or even removed. In this case, any changes to the exercise training program will be documented in the medical file.

Rules for stopping research

The rules for temporary cessation of the participation of a person in research or part or all of the research:

- 1) Anyone is free to temporarily stop participating in the research at any time.
- 2) Anyone can ask to temporarily interrupt their participation due to side effects of physical activity (pain, muscle fatigue ...).
- 3) Anyone may be temporarily unavailable for personal reasons.
- 4) A person who has not missed more than 3 consecutive sessions on the 4 weeks of the rehabilitation program can maintain their participation in the research if they wish.
- 5) The Supervisory Committee has the possibility to stop the search

The final stop rules:

- 1) Anyone is free to permanently stop his participation in research at any time without having to give reason.
- 2) Anyone with an incapacitating health problem that prohibits the practice of a physical activity will be excluded from research by decision of the investigator who will inform the coordinator, the rehabilitation team and the research manager.

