There are no plans to replace people who permanently stop the search. The data will be excluded from the statistical analysis. A temporary or permanent stop of the research will be automatically documented in the medical file.

Research Monitoring Committee

Research Monitoring Committee is composed of:

[name] (PU-PH, scientific manager)

[name] (Cardiologist, investigator)

[name] (PH, Scientific Officer)

[name] (Cardiologist, Scientific Officer)

[name] (PhD, Deputy Director of Clinique Saint Orens, project leader)

[name] (Teacher in Adapted [name] student, coordinator of the project)

The Research Monitoring Committee will meet 3 times: before the start of the research for the implementation visit, once 10 patients are included in the study, and at the end of the last end-of-study visit of the last patient. The Supervisory Committee ensures the smooth running of the research.

Ethical and regulatory compliance

Exams and methods used in this research are part of the routine care as defined by Law No. 2004-806 of 9 August 2004 (Article L1121-1, 2^o paragraph and Article R1121-3 of the Public Health Code). This study is a Clinical Routine Care Study

The instigator, the coordinator, and the investigators who drive and supervise the research undertake that this research is carried out in accordance with the law n° 2004-806 of August 9th, 2004, as well as in line with **Good Clinical Practice and the Declaration of Helsinki** (Ethical Principles for Medical Research Involving Humans, Tokyo 2004).

The research will be conducted in accordance with this protocol. Except in emergency situations requiring the implementation of specific therapeutic acts.

This research received the favourable opinion of the **Committee for the Protection of Persons** (ethical committee) (CPP) Sud-Ouest and Outremer II on May 6, 2015. This research is covered by the liability insurance of La Clinique Saint Orens.

The data recorded during this research are in accordance with the law n° 78-17 of January 6, 1978 relating to data, files and freedoms modified by the law 2004-801 of August 6, 2004. The Saint Orens Clinic will send a request for an opinion to the Advisory Committee on the Treatment of Information in the Field of Health Research (CCTIRS) and a request of authorization to the National Information Commissioner's Office / French Data Protection Authority (CNIL).

References

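### Adverse effects are recorded only if attributed to the training, so a cardiac event put down to the heart failure need not be recorded as an adverse event in either arm

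*Combined protocol and SAP*

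**What the plan says.** Under Specific terms of monitoring, the items to be noted begin with "Any adverse effects caused by physical exercise training (muscle pain cramp, fatigue of the patient". The same sentence goes on to "change of drug treatment, compliance with the protocol will be noted in the medical file". The first item carries a causal condition; the other two do not.

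Other records also carry no causal condition. If training is reduced or withdrawn for fatigue or for a medical reason, "any changes to the exercise training program will be documented in the medical file". At the end of the stopping rules: "A temporary or permanent stop of the research will be automatically documented in the medical file". The second final stop rule reads "Anyone with an incapacitating health problem that prohibits the practice of a physical activity will be excluded from research by decision of the investigator", and the investigator then informs the coordinator, the rehabilitation team and the research manager. The text following these rules adds that data of people who stop permanently are left out of the statistical analysis.

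On staffing, Rehabilitation Program: MICE and HIIT training mode says "Each session will be monitored by a physiotherapist and was supervised by a cardiologist". Blinding is stated only for the technician who reads the Holter recordings. On oversight, "a Supervisory Committee will ensure the proper conduct of research, the safety of proposed programs". The committee meets three times: before the start, after 10 inclusions, and at the end.

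The documents contain no definition of an adverse or serious adverse event, no causality scale, no named assessor of causality, no clinical safety endpoint and no planned table of adverse events by arm.

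**The concern.** In chronic heart failure the events that matter most for safety can arise from the disease as well as from hard exercise. The protocol's own background attributes nearly half of the deaths in this disease to rhythm disorders. When a patient decompensates or faints in week 2, cause is a matter of opinion. A rule that asks for that opinion before anything is written down makes the record depend on it. The examples given (muscle pain, cramp, fatigue) also steer the reader towards minor complaints.

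One arm trains in bouts at 100% of peak power output and the other continuously at 60%. Expected fallout says that a favourable result would support the feasibility of intense training in these patients and its possible later use at home. A reader will take that as partly a statement about safety. It needs a count of events that does not depend on what someone thought the cause was. If attribution differs between arms, the distortion could go either way, and an event that was never written down cannot reliably be recovered at analysis.

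**Working it through.** **1. The plan's own figure.** The plan has no safety figure. Its only sample-size figure is 16 per group, for night-time HFnu. Inputs from Sample Size: mean 31.5%, a change of about 11% read as relative, SD 3%, two-sided alpha 0.05, power 90%.
- Difference = 0.11 × 31.5 = 3.465.
- n = 2 × (1.960 + 1.282)² × 3² / 3.465² = 15.8, rounded up to 16 per group (normal-approximation power 0.904).

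The figure reproduces. It has no bearing on event capture beyond fixing the total at 2 × 16 = 32 patients.

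**2. Would a disease-attributed cardiac event be captured?**

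| Record | Condition for entry | What it shows of such an event |
|---|---|---|
| Adverse effects | Caused by the training | Nothing required |
| Drug changes | None | The change, if there is one |
| Training changes | Fatigue, medical or paramedical reason | The change, if there is one |
| Temporary or permanent stop | None | The stop; the patient need not give a reason for a permanent one |
| Exclusion for an incapacitating health problem | Investigator's decision | The exclusion; three parties are informed |
| Holter arrhythmias (secondary endpoint) | None; read blind | Only arrhythmias in two 24-h windows, D0 and W4, with exercise avoided |

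The second to fifth rows record consequences of an event. None requires its date, nature, seriousness or presumed cause. An event with no such consequence need not appear. The Holters cover neither the training sessions nor the weeks between the recordings.

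**3. Who judges cause?** No section says. The physiotherapist and cardiologist at the sessions can see which training is given, and neither is described as blinded. That the judgement would be made knowing the arm is therefore inferred.

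**4. Scale, by assumption only.** The documents give no event rate. Suppose a true cardiac event risk p per patient, and a fraction f of events attributed to exercise. Expected recorded events per arm = 16 × p × f. Chance that an arm records none = (1 − p × f)^16.

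| Assumed p | Expected events | Recorded if f = 0.5 | P(none recorded), f = 1 | P(none recorded), f = 0.5 |
|---|---|---|---|---|
| 5% | 0.8 | 0.4 | 44% | 67% |
| 10% | 1.6 | 0.8 | 19% | 44% |
| 20% | 3.2 | 1.6 | 3% | 19% |

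If attribution also differed by arm, say f = 0.5 in one and 0.25 in the other at p = 10%, the expected recorded counts would be 0.8 and 0.4 although the true risks are equal. These figures show the mechanism; they do not estimate its size in this trial.

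**5. A figure that does not measure the problem.** No events in 16 patients gives a one-sided 95% upper bound of 1 − 0.05^(1/16) = 17.1%. That reflects the size of the arm and would be the same with complete capture.

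**The case against.** The strongest reply is that the protocol is not blind to these events. A decompensation that changed drugs, training or participation would leave a required entry in the medical file whatever its presumed cause. An incapacitating problem is also reported to three parties. Arrhythmias are a secondary endpoint that needs no attribution and is read blind. A reader might infer from the recording rule that a cardiac event blamed on the disease leaves no record at all. The documents do not support that.

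Two other stronger readings also fail. A reader might infer that staff who know the arm make the causal judgement; no assessor is named, so this is an inference, and nothing in the documents speaks to anyone's motive. A reader might also infer that a planned HIIT–MICE safety comparison is biased; no such comparison is planned. The background figure, "up to 40% of CHF patients die within one year of their first hospitalization", cannot serve as an event rate here either. The trial enrols stable patients with no major cardiovascular event or procedure in the preceding 3 months.

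What remains is that indirect traces are not an event record, the Holters miss the training period, and no rule requires an event to be recorded whatever its cause. The general commitment to Good Clinical Practice under Ethical and regulatory compliance is not turned into a recording procedure.

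**Conclusion.** The point holds in a limited form. Followed exactly, the rule makes causation by training a condition for noting an adverse effect. A decompensation, syncope, hospitalisation or between-Holter arrhythmia attributed to the disease need not be recorded as an adverse event. Any later statement on the safety or feasibility of HIIT against MICE would rest on an attribution-filtered record. So would the committee's oversight, if it works from these entries; the documents do not say what it reviews.

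The size of the effect cannot be stated, because the documents give neither an event rate nor an attribution rate. Its direction is also open. It should not be read as showing that events will be lost without trace or that attribution will in fact be unblinded. The primary endpoint is not affected by the recording rule itself. The separate rule that drops the data of patients who stop permanently makes the gap wider, since patients with the most serious events may be among them. The change is worth making because it is cheap and what is not recorded cannot reliably be recovered.

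**What to change.** Replace the adverse-effect clause under Specific terms of monitoring with a rule along these lines: all adverse events, whatever their presumed cause, including decompensation, arrhythmia, syncope, hospitalisation and death, are recorded from randomisation to the end of a stated window. Date, seriousness and relation to exercise are separate fields. Name who judges relation to exercise and, where possible, have it judged without knowledge of the arm.

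State the window. Research Calendar gives 7 months of participation, of which 4 weeks are in the centre, and the follow-up table shows no visit after Week 4. Either period can be used, but the protocol must say which.

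Add to Statistical analyses a descriptive table of all adverse events by randomised arm, with exercise-related events in a second column. State that events in patients who permanently stop stay in this table, despite the rule that their data are excluded from the statistical analysis. Say that the committee receives the same list.

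The cost is a few sentences and a short form per event in about 32 patients. Some unrelated events will appear in the listing. The 7-month window would mean extra follow-up work, since no contact after Week 4 is scheduled. Training, endpoints and sample size are unchanged.

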Several studies have shown a reduction of the sympathetic activity measured by microneurography (MSNA) after an exercise training program in heart failure [19, 20]. This is also found on other ANS parameters such as the Heart Rate Variability that is improving [6, 9]. Catecholamines also tends to decrease with aerobic activity [21]. This improvement in vegetative balance is associated with an improvement in the different vegetative reflexes involved in the regulation of cardiovascular ANS. Thus, the abnormalities noted on the baroreflex, the chemoreflex, the ergoreflex and the central control are all potentially improved by repeated aerobic exercise [22, 23]. Thus the sympathetic stimulation induced during the exercise is followed by a period of increase in vagal tone, explaining the benefit on the rhythmic profil . To our knowledge there is no study comparing the effects on the ANS of MICE training versus HIIT training in CHF.

Hypothesis

Our team recently used an intermittent exercise protocol that has been optimized in CHF patients [24] in order to induce a strong cardiovascular and muscular stimulus while ensuring safety and comfort of the patient (30 seconds at 100% of peak power alternate with 30 sec of passive recovery). In 18 CHF patients, we showed that a single intermittent exercise session increases parasympathetic tone (high frequency index in normalized units HFnu%) and significantly decreases premature ventricular contraction within the 24h of the exercise, compared to a single session of MICE [16]. These results appear promising and suggest that stimuli associated with intense intermittent exercise and passive recovery, as opposed to continuous-type exercise of moderate intensity, would be more effective to increase sympatho-vagal balance and arrhythmias. Nevertheless, the effects of a several weeks of an HIIT program on explanatory parameters of sudden death (SNA activity, arrhythmias, cardiac function) have never been studied in CHF patients. We therefore hypothesize that HIIT is superior to MICE for 1/ increasing parasympathetic activity measured by HRV, 2 / the cardiorespiratory fitness. In addition, we also hypothesize that there is a link between improved physical capacity and vagal tone and decreased arrhythmias.

Objectives

Main objective:

To compare, in patients with chronic heart failure, the efficacy of 4-weeks exercise training programs (MICE vs HIIT) on the evolution of the spectral high frequency (HF) component of HRV.

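### Continued participation depends on consecutive absences, with no stated consequence for exceeding the limit; if that counts as a permanent stop, randomised patients are dropped from the analysis

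*Combined protocol and SAP*

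**What the plan says.** Rule 4 under Rules for stopping research, in the list on temporary cessation, states: "A person who has not missed more than 3 consecutive sessions on the 4 weeks of the rehabilitation program can maintain their participation", if the person wishes. No other attendance criterion appears in the combined protocol and SAP. There is no minimum number of sessions, and the Statistical analyses section defines no analysis population.

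The final stop rules list two grounds: voluntary permanent withdrawal, and an incapacitating health problem that rules out physical activity. Missing four or more sessions in a row is not among them. The text after that list says: "There are no plans to replace people who permanently stop the search. The data will be excluded from the statistical analysis".

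Under Specific terms of monitoring, "the exercise training intensity may be reduced or even removed" in some circumstances, with documentation, and "compliance with the protocol will be noted in the medical file". No analysis uses that information.

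The Rehabilitation Program section says "the RP last 3 hours per day, 5 days per week during 3.5 weeks". The main objective and rule 4 both speak of 4 weeks.

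**The concern.** A condition for staying in the research implies that someone who fails it may not stay in. The protocol leaves that consequence unstated, so the site must decide. If it decides on a permanent stop, the data exclusion follows.

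Whether a randomised patient is analysed would then turn on something that happens after randomisation and may be related to the arm: a demanding interval programme and a moderate continuous one need not produce the same absences. The people running the sessions know which training each patient receives. Blinded reading of the Holter recordings protects the measurement, but not the selection of who is measured.

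The rule is also a poor proxy for exposure. It looks at the longest run of absences and ignores the total, so it can separate patients in the reverse order of training received. With 16 per arm, no replacement and no stated allowance for dropout, a few exclusions matter.

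**Working it through.** **1. The plan's sample size.** Inputs from the Sample Size section: mean HFnu 31.5%, change of about 11%, SD 3%, power 90%, two-sided alpha 0.05, 16 per group. Reading 11% as relative, the difference is 0.11 × 31.5 = 3.465 points.

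n per group = 2 × (1.960 + 1.282)² × (3 / 3.465)² = 15.8, rounded up to 16.

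The stated figure is reproduced. A t-based calculation gives 17. Reading 11% as 11 absolute points gives 2 to 3 per group, which does not match.

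**2. Number of sessions.** Assume that a session in rule 4 means the daily cycling session, one per programme day. Five days a week for 3.5 weeks is 17.5, so 17 or 18. Five days a week for 4 weeks is 20.

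**3. What the rule admits and does not admit.** The fewest sessions attended without a run of more than 3 absences comes from repeatedly missing three and attending one, which gives the whole-number part of n/4. A patient whose only absence is a single run of four attends n − 4.

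| Planned sessions | Fewest attended, limit met | One four-session gap, limit exceeded |
|---|---|---|
| 17 | 4 (23.5%) | 13 (76.5%) |
| 18 | 4 (22.2%) | 14 (77.8%) |
| 20 | 5 (25.0%) | 16 (80.0%) |

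**4. Power if patients are excluded.** Two-sample t-test, difference 3.465, SD 3, two-sided 5%, equal losses in each arm. Noncentrality = 3.465 / (3 × √(2/n)), with 2n − 2 degrees of freedom.

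| Per arm | Lost per arm | Noncentrality | Power (t) | Power (z) |
|---|---|---|---|---|
| 16 | 0 | 3.27 | 88.5% | 90.4% |
| 14 | 2 (12.5%) | 3.06 | 83.7% | 86.3% |
| 12 | 4 (25%) | 2.83 | 77.2% | 80.8% |

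The gap between 88.5% and the planned 90% comes from using t instead of z and has nothing to do with rule 4.

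**5. Bias.** No size can be given. It depends on how absences differ between arms and how they relate to HFnu, and the documents are silent on both.

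**The case against.** The strongest reply is that the protocol never says that a patient who exceeds the limit is out. Rule 4 is permissive, sits among the temporary interruptions, and is not repeated in the final stop rules. The data exclusion, read in context, concerns people who stop permanently. This stands: exclusion is the converse of rule 4, not its text. A reader might infer that the plan expels someone with about 80% attendance, and the documents do not go that far. What remains is that a condition without a stated consequence invites differing handling, and one plausible handling leads to exclusion.

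A reader might also infer that the analysed sample does not represent the programmes. That is not shown. The pattern giving 22 to 25% attendance is the extreme that the rule permits, and no expected attendance is given.

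Finally, one might cite dilution as the harm. If 2, 3 or 4 of 16 per arm attended a quarter of sessions and the effect were proportional to attendance (both assumptions), the difference would be 3.465 × (1 − 0.75 × k/16) = 3.14, 2.98 or 2.82 points, and t-test power 81.7%, 77.5% or 72.9%. But those figures come from keeping low attenders. Keeping them is what an analysis of all randomised patients does, and the change recommended here keeps them too. They are not a harm that it removes.

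It is also fair to say that rule 4 does damage only through the exclusion of permanent stoppers. An analysis of everyone randomised would make it largely harmless, which is why the remedy centres on that.

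**Conclusion.** The point holds as a gap in the rules with a conditional consequence. Rule 4 ties participation to consecutive absences, says nothing about what follows from exceeding three, and does not track exposure: 22 to 25% attendance can satisfy it, while 76 to 80% with one four-session gap does not.

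If exceeding the limit is handled as a permanent stop, the plan excludes randomised patients on an event after randomisation, without replacement. The comparison can then be biased if absences differ by arm. Two exclusions per arm would cost about 5 points of power (88.5% to 83.7%), and four would cost about 11 (to 77.2%).

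This rests on one cycling session per programme day, the planned difference and SD being right, and equal losses per arm. The losses are illustrations, not forecasts.

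**What to change.** State that a patient's pattern of absence does not end participation in the research. Carry out the Week 4 assessments in every randomised patient who still consents, and analyse all of them in the primary analysis in the group to which they were randomised.

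Record the total number of cycling sessions completed. If a supporting adherence analysis is wanted, define it before the data are analysed by a pre-stated share of total planned sessions, and label it non-randomised, because it selects patients after allocation. It is optional.

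Reconcile the 3.5-week and 4-week descriptions of the programme, since any share of planned sessions needs a fixed denominator.

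The cost is a short protocol change, a session count and some additional Week 4 visits. Compliance is already to be noted in the medical file and sessions are monitored by a physiotherapist, but the documents do not say that a count is kept. The downside is that low attenders, including some with long unbroken absences, stay in and may dilute the contrast. Clinical decisions to pause or alter training are outside this point.
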